1. GVHD
2. Secondary graft failure

Serious Adverse Event Reporting (SAE) for MD Anderson-Sponsored IND Protocols

An adverse event or suspected adverse reaction is considered “serious” if, in the view of either the investigator or the sponsor, it results in any of the following outcomes:

- Death
- A life-threatening adverse drug experience – any adverse experience that places the patient, in the view of the initial reporter, at immediate risk of death from the adverse experience as it occurred. It does not include an adverse experience that, had it occurred in a more severe form, might have caused death.

- Inpatient hospitalization or prolongation of existing hospitalization
- A persistent or significant incapacity or substantial disruption of the ability to conduct normal life functions.
- A congenital anomaly/birth defect.

Important medical events that may not result in death, be life-threatening, or require hospitalization may be considered a serious adverse drug experience when, based upon appropriate medical judgment, they may jeopardize the patient or subject and may require medical or surgical intervention to prevent one of the outcomes listed in this definition.

Examples of such medical events include allergic bronchospasm requiring intensive treatment in an emergency room or at home, blood dyscrasias or convulsions that do not result in inpatient hospitalization, or the development of drug dependency or drug abuse (21 CFR 312.32).

- Important medical events as defined above, may also be considered serious adverse events. Any important medical event can and should be reported as an SAE if deemed appropriate by the Principal Investigator or the IND Sponsor, IND Office.
- All events occurring during the conduct of a protocol and meeting the definition of a SAE must be reported to the IRB in accordance with the timeframes and procedures outlined in “The University of Texas M. D. Anderson Cancer Center Institutional Review Board Policy for Investigators on Reporting Unanticipated Adverse Events for Drugs and Devices”. Unless stated otherwise in the protocol, all SAEs, expected or unexpected, must be reported to the IND Office, regardless of attribution (within 5 working days of knowledge of the event).
- All life-threatening or fatal events, that are unexpected, and related to the study drug, must have a written report submitted within 24 hours (next working day) of knowledge of the event to the Safety Project Manager in the IND Office.
- Unless otherwise noted, the electronic SAE application (eSAE) will be utilized for safety reporting to the IND Office and MDACC IRB.
- A copy of the eSAE report will also be sent to [name] ([contact]) and to Revlimid ([contact]), the supporter of CTY-107.
- Serious adverse events will be captured from the time of the first injection of CYT107 through 30 days from the last injection. Serious adverse events must be followed until clinical recovery is complete and laboratory tests have returned to baseline, progression of the event has stabilized, or there has been acceptable resolution of the event.
- Additionally, any serious adverse events that occur after the 30 day time period that are related to the study treatment must be reported to the IND Office. This may include the development of a secondary malignancy.

Reporting to FDA

- Serious adverse events will be forwarded to FDA by the IND Sponsor (Safety Project Manager IND Office) according to 21 CFR 312.32.

It is the responsibility of the PI and the research team to ensure serious adverse events are reported according to the Code of Federal Regulations, Good Clinical Practices, the protocol guidelines, the sponsor's guidelines, and Institutional Review Board policy.

AEs Attribution Assessment

Events assessed as to be caused by the administration of CYT107 and its direct consequences will be assessed as definite related.

When the relationship of the adverse event cannot be ruled out between the CYT107 and the drugs used as part of the treatment plan, as well as for GVHD, infections and supportive treatment, the event will be scored as probably or possible related.

The principal investigator will be the final arbiter in determining the causality assessment.

AEs Severity Assessment

AEs will be assessed according to the NCI Common Terminology Criteria for Adverse Events (CTCAE) version 4.0.

Events not included in the CTCAE version 4.0 will be scored as follows:

General grading:

Grade 1: Mild: discomfort present with no disruption of daily activity, no treatment required beyond prophylaxis.

Grade 2: Moderate: discomfort present with some disruption of daily activity, require treatment.

Grade 3: Severe: discomfort that interrupts normal daily activity, not responding to first line treatment.

Grade 4: Life Threatening: discomfort that represents immediate risk of death.

AEs Data Collection

Redcap/Core will be used as the electronic database/case report form (CRF) for this protocol.

During the active treatment period, expected and unrelated adverse events considered unexpected and related to CYT107 will be collected in electronic medical record (EPIC). SAEs and AEs that require dose modifications will be captured in REDCap. The data will reflect the onset and resolution date and maximum grade. Intermittent events should be labeled as such and followed until resolution. If a patient is taken off study while an event still ongoing, this will be followed until resolution or the event has stabilized. Pre-existing medical conditions will be recorded only if an exacerbation occurs during the ATP. Co-morbid events will not be scored and collected separately.

Medical events not considered adverse events will not be documented in the CRF. They will be captured in the medical record.

- All events occurring during the conduct of a protocol and meeting the definition of a SAE must be reported to the IRB in accordance with the timeframes and procedures outlined in "The University of Texas M. D. Anderson Cancer Center Institutional Review Board Policy for Investigators on Reporting Serious Unanticipated Adverse Events for Drugs and Devices". Unless stated otherwise in the protocol, all SAEs, expected or unexpected, must be reported to the IND Office, regardless of attribution (within 5 working days of knowledge of the event).

- All life-threatening or fatal events, that are unexpected, and related to the study drug, must have a written report submitted within 24 hours (next working day) of knowledge of the event to the Safety Project Manager in the IND Office.
- Unless otherwise noted, the electronic SAE application (eSAE) will be utilized for safety reporting to the IND Office and MDACC IRB.
A copy of the eSAE will also be sent to RevImmune, the supporter of CYT-107.
- Serious adverse events will be captured from the time of the first protocol-specific intervention, until 30 days after the last dose of drug, unless the participant withdraws consent. Serious adverse events must be followed until clinical recovery is complete and laboratory tests have returned to baseline, progression of the event has stabilized, or there has been acceptable resolution of the event.
- Additionally, any serious adverse events that occur after the 30 day time period that are related to the study treatment must be reported to the IND Office. This may include the development of a secondary malignancy.
- Patients who withdraw consent due to toxicities will be evaluable and considered treatment failures.

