4.0 Treatment Plan and Study Design

CYT107 will not be administered before Day 60 but could be started as late as Day 180 post-CBT or haplo-SCT.

The active treatment period will be from the first injection of CYT107 and for 30 days after the last injection. The follow-up period will be for three years after the last injection.

Patients will be treated with CYT107 by intramuscular route (I.M.)* post CBT or haplo-SCT (from 60 to 180 days), with 1 of 3 doses below:

- 5 mcg/kg/dose for 3 doses, one week apart
- 10 mcg/kg/dose for 3 doses, one week apart
- 20 mcg/kg/dose for 3 doses, one week apart

Enrollment of the first 3 participants will be staggered by 14 days. Accrual in between cohorts will be halted for 30 days after the last patient in each cohort has received the last dose of CYT107.

* If the patient's platelet count is below 35,000, the product may be administered by subcutaneous route.

All patients will receive foscarnet for the management of CMV infection as per Stem Cell Transplantation and Cellular Therapy Department's standard of care.

Dose modifications

Treatment will be permanently discontinued for patients developing grade 3 or 4 GVHD, secondary graft failure, disease relapse, PTLD, PML, grade 2-4 skin rash, or grade 3-4 non-hematological toxicity attributable to CYT107.

Patients who develop grade 2 non-hematological toxicity attributable to the CYT107 will have the next dose withheld until the toxicity resolves to grade 1. If the toxicity resolves within 2 weeks the drug will be administered at the same dose, however if the toxicity takes more than 2 weeks to resolve the drug will be administered at the next lower level, or permanently discontinued if the patient was already at the lowest level. If the toxicity takes more than 4 weeks to improve to grade 1, the CYT107 will be permanently discontinued

For patients who at study entry have grade 0, 1 or 2 hematological toxicity and develop grade IV hematological toxicity attributable to the CYT107 will have the next dose withheld until the toxicity resolves to grade 2. If the toxicity resolves within 2 weeks the drug will be administered at the same dose, however if the toxicity takes more than 2 weeks to resolve the drug will be administered at the next lower level, or permanently discontinued if the patient was already at the lowest level. If the toxicity takes more than 4 weeks to improve to grade 2, the CYT107 will be permanently discontinued

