7.0 Statistical Considerations

7.1 Outcomes and Covariates

7.1.1 Primary Outcomes

Toxicity. Dose limiting toxicity (DLT) is defined as any of the following events: grade 3 or 4 GVHD, secondary graft failure, disease relapse, development of PTLD, development of PML, grade 2 organ failure or grade 2-4 skin rash, fatigue, AST and ALT elevations, allergic anaphylaxis, or hemolytic anemia, attributable to CYT107, or death, occurring within 42 days of the first CYT107 injection.

Biological Responses. The absolute number and percentage of total White Blood Cells (WBCs) consisting of T-cells and of B-cells will be observed at 1, 3, 6, 9 and 12 months.

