9.0 Adverse Events and Reporting Requirements

Adverse event definition:

An adverse event is the appearance or worsening of any undesirable sign, symptom, or medical condition occurring after starting the study drug even if the event is not considered to be related to study drug. Medical conditions/diseases present before starting study drug are only considered adverse events if they worsen after starting study drug. Abnormal laboratory values or test results constitute adverse events only if they induce clinical signs or symptoms, are considered clinically significant, or require therapy and otherwise meet the criteria for a reportable adverse event as defined above. They are to be captured under the signs, symptoms or diagnoses associated with them.

It is common for HCT recipients to experience multiple complications as part of the transplant itself that are unrelated to exposure to investigational agents. Symptoms of the original or targeted disease are not to be considered adverse events for this study except for hematological toxicities as defined below. From start of study treatment through 30 days from last dose of CYT107, symptoms related to the conditioning regimen will not be reported unless the event is both serious and considered by the investigator to also be possibly, probably, or definitely related to CYT107. After 30 days from the last dose of CYT107, adverse events should only be reported if they are both serious and probably or definitely related to CYT107. Events that are unlikely or unrelated to CYT107 are not required to be reported. Reporting of such events should include the investigator's assessment as to whether the event should be attributed to any of the HCT procedure itself, CYT107, GVHD, or exposure to immunosuppressive agents. An event may be attributable to all, some, or one of these categories.

Assessment of the Adverse Events Severity:

The severity of the adverse events (AEs) will be graded according to the Common Terminology Criteria v4.0 (CTCAE).

Recommended Adverse Event Recording Guidelines

Attribution	Grade 1	Grade 2	Grade 3	Grade 4	Grade 5
Unrelated	Phase I	Phase I	Phase I Phase II	Phase I Phase II Phase III	Phase I Phase II Phase III
Unlikely	Phase I	Phase I	Phase I Phase II	Phase I Phase II Phase III	Phase I Phase II Phase III
Possible	Phase I Phase II	Phase I Phase II Phase III			
Probable	Phase I Phase II Phase III				
Definitive	Phase I Phase II Phase III				

Treatment period:

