Active treatment period (ATP) is defined from the first injection of CYT107 through 30 days from

the last injection.

Time for Adverse Event (AE) Collection:

Adverse events will be collected from the first injection of CYT107 through 30 days from the last injection. AEs that occur up to 30 days from the last injection of CYT107 will be followed until resolution.

The collection of adverse events will reflect the onset and resolution date and maximum grade. If a patient is taken off study while an event is still ongoing, this will be followed until resolution or the event has stabilized. Pre-existing medical conditions will be recorded only if an exacerbation occurs during the active treatment period. Co-morbid events will not be scored separately.

Adverse Event Reporting:

The Investigator or physician designee is responsible for verifying and providing source documentation for all adverse events, and assigning attribution for each event on all subjects enrolled on this study.

Adverse events will be documented and entered into the electronic case report form (REDCap/CORe). All protocol specific data will be entered into REDCap/CORe.

Events not to be considered adverse events in this study are those related to original disease or expected in the post-allogeneic transplant period.

Isolated changes in laboratory parameters such as electrolyte, magnesium and metabolic imbalances, uric acid changes, elevations of GPT, GOT, LDH and alkaline phosphatase will not be captured.

Concomitant medications

Patients treated on this protocol will require supportive care treatment (concomitant medications). These medications are considered standard of care and have no scientific contribution to the protocol; therefore no data will be captured on various medications needed or their side effects. All concomitant medications will be captured in the medical record.

Causality Assessment.

The principal investigator will be the final arbiter in determining the causality assessment.

List of most common expected adverse events:

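### The adverse event recording rules in Section 9.0 conflict with each other and with the DLT definition, so some DLTs may lack a record in the trial database

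*Combined protocol and SAP*

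**What the plan says.** Section 7.1.1 makes DLT a primary outcome. Its components include grade 3 or 4 GVHD, secondary graft failure, relapse, death and a group that need not be serious: "grade 2 organ failure or grade 2-4 skin rash, fatigue, AST and ALT elevations, allergic anaphylaxis, or hemolytic anemia, attributable to CYT107". The window covers events "occurring within 42 days of the first CYT107 injection".

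Section 9.0 names REDCap/CORe as the database and case report form, then says different things about what goes into it:

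- Adverse Event Reporting: "Adverse events will be documented and entered into the electronic case report form (REDCap/CORe"), with no limit by seriousness or effect on dosing, and "All protocol specific data will be entered into REDCap/CORe".
- The same subsection says that events related to the original disease or expected after allogeneic transplant are not adverse events, and that isolated laboratory changes, including GPT and GOT elevations, are not captured.
- AEs Data Collection: "expected and unrelated adverse events considered unexpected and related to CYT107 will be collected in electronic medical record (EPIC"), followed by "SAEs and AEs that require dose modifications will be captured in REDCap". It adds that medical events not considered adverse events stay out of the case report form.

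Treatment in Section 4.0 is three injections at weekly intervals (for the lowest level, "5 mcg/kg/dose for 3 doses, one week apart"). For grade 2 non-hematological toxicity, the dose-modification rule acts on the next dose.

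**The concern.** The two subsections cannot both be followed. One sends adverse events to the database without a filter on seriousness. The other splits them between the medical record and the database. The sentence on the medical record cannot be applied as written, because it describes the same events as expected and unrelated and also as unexpected and related.

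The split matters because several DLT components can occur without being serious and without changing a dose. The exclusions under Adverse Event Reporting matter for a different reason: they remove events that Section 7.1.1 counts. Both bear on the DLT count, which supports the primary safety conclusion and the within-dose stopping rule in Section 7.3.2. With at most 7 patients per dose under the base allocation, one DLT can decide whether a boundary is crossed.

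**Working it through.** **Step 1. Which DLTs have no route into REDCap under AEs Data Collection?** On schedule the injections fall on days 0, 7 and 14. The DLT window ends on day 42, so 42 − 14 = 28 of 42 days (67%) follow the last injection. A grade 2 fatigue on day 30 that is attributable to CYT107 is a DLT. It is not an SAE unless it meets a seriousness criterion, and no next dose remains to withhold. It therefore has no adverse-event route into REDCap under this rule. The 67% is a share of days, not of events, and withheld doses would shorten the period. The collection period is not the cause: after three injections on schedule it runs to day 14 + 30 = 44, past the window.

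The gap is not confined to the time after the third injection. The hematological dose-modification rule in Section 4.0 starts at grade IV, so a non-serious hemolytic anemia below that grade, if handled under that rule, may trigger no modification at any time.

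**Step 2. Which DLTs meet the exclusions under Adverse Event Reporting?**

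| DLT component (Section 7.1.1) | Conflicting text (Section 9.0) |
|---|---|
| Attributable AST/ALT elevation | Isolated GPT/GOT elevations are not captured |
| Disease relapse | Events related to the original disease are not adverse events |
| Grade 3 or 4 GVHD | Events expected post-transplant are not adverse events; GVHD also heads the list of expected adverse events |

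The AST/ALT exclusion applies at any time. Before the last injection the two subsections can even point in opposite directions: an attributable grade 2 elevation that leads to a withheld dose is admitted by one and, if isolated, barred by the other.

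**Step 3. What depends on a complete count?** Section 7.3.2 uses a beta(.35, .65) prior and stops a dose if Pr[p(d) > .35 | data] > .85, from n = 3. The posterior probability exceeds .85 at 3/3 (.985), 3/4 (.932), 4/5 (.973) and 4/6 (.929), but not at 2/3 (.834) or 3/5 (.849). A stop at n = 7 saves no accrual. With q = 1 − p, enumerating the paths gives

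Pr(stop before patient 7) = p³ + 3p³q + 6p⁴q².

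- p = .35: .0429 + .0836 + .0380 = .165 (plan .163)
- p = .55: .1664 + .2246 + .1112 = .502 (plan .497)
- p = .60: .2160 + .2592 + .1244 = .600 (plan .601)

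These three rows of the plan's table reproduce. The fourth (p = .65) gives .694 against a stated .607; that is a separate matter.

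**Step 4. Sensitivity to lost DLTs (assumption).** The documents do not say what share f of DLTs might be lost. If each DLT is lost independently with probability f, and the rule is run on what remains, p is replaced by p(1 − f). For p = .55 and f = 10%, p becomes .495 and the result is .1213 + .1838 + .0919 = .397.

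| Share lost | True .35 | True .55 | True .60 |
|---|---|---|---|
| 0 | .165 | .502 | .600 |
| 10% | .123 | .397 | .483 |
| 20% | .088 | .299 | .369 |
| 33% | .052 | .186 | .234 |
| 50% | .022 | .084 | .108 |

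**The case against.** The strongest reply is that the DLT count need not come from adverse-event entries at all. Section 6.2 schedules weekly adverse event assessment to day +42. Section 7.6 makes the investigator and designated staff responsible for recording outcome variables and applying the DLT rule. Section 7.7 requires toxicity summaries after specified numbers of patients have completed 42 days. Section 9.0 sends all protocol-specific data to REDCap/CORe, and DLT status is surely such data. Even under AEs Data Collection, other events are kept in the medical record, and the sentence on REDCap does not contain the word *only*.

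Most of this stands. A reader might infer that non-serious DLTs after the third injection would certainly go uncaptured and that the trial would undercount DLTs. The documents do not support that: the inference needs the restrictive rule to be followed and the other routes to fail. What remains is that Sections 7.6 and 7.7 name no database and do not lift the filters in Section 9.0, and the general sentence on protocol-specific data does not say that it overrides the specific exclusions beside it.

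Rash is a poor example, because grade 2-4 rash is also a trigger for permanent discontinuation (Section 4.0) and for removal (Section 8.0), so a site might well enter it. Fatigue and AST/ALT elevation are the clearer cases.

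A reader might also see a contradiction between the sentence "Events that are unlikely or unrelated to CYT107 are not required to be reported" and the Phase I columns of the recording table in Section 9.0. That reading is weak. The sentence follows a rule for the period beyond 30 days after the last dose and may be limited to it. The table is headed as a recommendation. The potentially non-serious DLT components must be attributable to CYT107, so leaving out unrelated events would not remove them.

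**Conclusion.** The inconsistency is real and touches the primary safety outcome. Two subsections of Section 9.0 disagree on what enters the database, one sentence cannot be applied as written, and the exclusions overlap with listed DLT components. The supportable consequence is that some DLTs may lack an adverse-event record in REDCap/CORe.

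Its size cannot be fixed from the documents. The stopping probabilities show sensitivity only: at a true rate of .55, a loss of 10% or 20% would move the chance of stopping from about .50 to .40 or .30. They assume that DLTs are lost at random and that the rule is run on database records, which the plan does not state. Several components, such as death, PTLD, PML and anaphylaxis, would usually be serious and so captured under either rule, which limits the plausible loss. The point should be corrected, but it does not show that the stopping rule fails.

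**What to change.** Reconcile Section 7.1.1 with the Adverse Event Reporting and AEs Data Collection parts of Section 9.0. State that every event on the DLT list occurring within 42 days of the first injection is entered in REDCap/CORe, whether or not it is serious, changes dosing, is laboratory-only or is expected after transplant. Make the exclusions for isolated laboratory changes, disease-related events and expected post-transplant events subject to that sentence. Rewrite the medical-record sentence so that it names one identifiable class of events.

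There is no need to enter all adverse events of every grade and attribution. That would be a preference, and on its own it would leave the conflicting exclusions in place.

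The cost is amendment wording and minor data entry for at most 21 patients.
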